#### 5.16 Heart Rhythm Monitoring

ECG, Transtelephonic monitors (TTM) and 24 Hour Holter Monitoring will be used to monitor the subjects' heart rhythm post-treatment.

#### **Electrocardiogram (12-lead ECG):**

ECG device will be provided to each site. Sites will be instructed to record and transmit for every subject per the schedule of treatment and evaluations summarized in Table 5-1.

#### **Transtelephonic Monitors (TTM):**

Transtelephonic monitors (TTM) will be provided to each subject at the 1-month followup visit for scheduled transmissions of heart rhythm status. Subjects will be instructed to transmit all emergent symptomatic cardiac events and follow a detailed schedule if the subject remains asymptomatic post ablation during the last 2 months of the blanking period and the Evaluation Period (Day 91-365).

The TTM transmission schedule:

- Each subject will be provided with a TTM device at the 1-month visit.
- Subjects will complete a test transmission upon receipt of the TTM device to demonstrate a working understanding of the device.
- The TTM schedule will include 2 months of TTMs during the blanking period. At the 1-month office visit or during discharge, subjects will be provided a TTM for event monitoring during the follow-up period. The first transmission will be at the 1 month office visit. TTM schedule will be every week for months 2, 3, 4 and 5. After the weekly transmissions, subjects will be asked to record and transmit a minimum of 1 transmission (60 seconds) per month until the effectiveness

assessment period is completed (12 months post index procedure). In addition, subjects will also be asked to transmit any symptom-triggered episode that occurs during the 12-month follow-up period.

Months (post-procedure)	TTM schedule (asymptomatic)
Month 2, 3, 4, 5	1 per week
Month 6, 7, 8, 9, 10, 11, 12	1 per month

• All symptomatic cardiac episodes should be recorded and transmitted soon after the event occurs. A core lab will be used to evaluate and assess the TTM tracings.

## Holter Monitoring:

• A 24 Hour Holter will be used at the 12 month follow-up visit to monitor the subjects' heart rhythm. A core lab will be utilized to evaluate and assess the 24-hour Holter recordings.

#### 5.17 Study Equipment

#### 5.17.1 Required Catheters and Equipment

The following devices are required for the AF ablation procedure during this study:

Equipment	Function or Specifics
VISITAG SURPOINT™ Module Activation Kit (KT5400163)	Activiation of Software that the EPU uses to compute Tag Index values and communicate with the CARTO 3 System
VISITAG SURPOINT™ External Processing Unit (EPU) (D-1608-01)	EPU is a device that receives ablation data from the CARTO® 3 System Workstation (power, contact force, and duration), computes Tag Index values, and then returns the computed results for display in the CARTO® 3 System

 
Approved Catheter(s)
 
THERMOCOOL SMARTTOUCH® Catheter: 
 
Uni-directional Catheter Description (D-1336-OX-S)
 
Bi-directional Catheter Description (D-1327-OX-S)
 
 
 
THERMOCOOL SMARTTOUCH® SF Catheter: 
 
Uni-directional Catheter Description (D-1347-XX-S)
 
Bi-directional Catheter Description (D-1348-XX-S)
 
 
 
	Used to map, navigate, and deliver RF energy to the target tissue while providing the contact force measurement feedback.
SMARTABLATE RF Generator	Transmits radiofrequency energy to the THERMOCOOL SMARTTOUCH® SF and THERMOCOOL SMARTTOUCH® Mapping & Ablation Catheters
CARTO ® 3 V 6.0 System	For mapping and visualization information. Version 6.0.54.x or higher

## Table 5-2 Required Study Equipment

## 5.17.2 Recommendation for Irrigation Pump Setting and RF Power Delivery

The Irrigation Pump will deliver a continuous infusion of 2 ml/min of room temperature heparinized saline (1 u heparin/1 ml saline) when not delivering RF current. Operators should increase the irrigation to high flow rate starting up to 5 seconds before the onset of RF energy delivery and maintain this higher flow rate until 5 seconds after termination of the energy application. For THERMOCOOL SMARTTOUCH®SF Catheter, for power levels up to 30 W, a high flow rate of 8 ml/min should be used. For power levels between 31 and 45 W, a high flow rate of 15 ml/min should be used. Do not use this catheter without irrigation flow. For THERMOCOOL SMARTTOUCH® Catheter, for power levels up to 30 W, a high flow rate of 17 ml/min should be used. For power levels up to 30 W, a high flow rate of 17 ml/min should be used. For power levels up to 30 W, a high flow rate of 17 ml/min should be used. For power levels up to 30 W, a high flow rate of 17 ml/min should be used. For power levels up to 30 W, a high flow rate of 17 ml/min should be used. For power levels up to 30 W, a high flow rate of 17 ml/min should be used. For power levels up to 30 W, a high flow rate of 17 ml/min should be used. For power levels between 31 and 45 W, a high flow rate of 10 ml/min should be used. For power levels between 31 and 45 W, a high flow rate of 30 ml/min should be used.

Treatment of AF: It is recommended that power not exceed 45 W and 35 W if the catheter is perpendicular to the tissue. Refer to the IFU Summary of Clinical Studies for lesion recommendations.

Power*	Irrigation Flow Rate
Maintenance Flow	2 ml/min
≤ 30 W	8 ml/min
31-45 W	15 ml/min

 Table 5-3 Recommended RF Energy Delivery Parameters

\* Reduce power at start of ablation. Power titration should be used for all applications of RF to achieve the desired result. Refer to the IFU or THERMOCOOL SMARTTOUCH® SF AND THERMOCOOL SMARTTOUCH® training slides for usage of catheters.

#### 5.17.3 Investigator Training

#### **SMARTTOUCH SF Catheter Training:**

Investigators selected to participate in the study will be skilled in intracardiac mapping and AF ablation with THERMOCOOL SMARTTOUCH® and THERMOCOOL SMARTTOUCH® SF catheters (>20 cases). They will provide 5 Retrospective PAF cases with segmented VISITAGTM (9 regions) with their standard workflow. Investigators will undergo device training in accordance with the documented physician training plan.

#### VISITAG SURPOINTTM Module:

The purpose of the individual training process is to identify the Tag index value which best represents the physician's ablation strategy, per anatomical ablation segment.

- The process:
  - o Is individual,
  - Maintains the physician's ablation strategy catheter, force, power, time, etc.
  - Optimizes the system settings to have exactly one tag per RF application and location,
  - o displaying the tag as early as possible, emphasizing on catheter tip stability.
  - Requires at least 5 retrospective cases, blinded to the Tag Index
  - Provides descriptive statistical analysis of Tag Index values, per segment.
  - Ends with the physician selecting his/hers own Tag index values.
- Based on literature review, we recommend the following Tag Index target Values:
  - 380 on the posterior and inferior
  - 550 on the anterior, roof and ridge

#### FIGURE 5.17.3A: An example of retrospective analysis:

Anatomical Segment Locations

VISITAG SURPOINT Tag Index Values

[figure not shown]

TABLE 5-5: An Example of Retrospective VISITAG SURPOINT Tag Index Values

Segment	Posterior	Inferior	Anterior	Roof	Ridge
Count	47	23	23	21	6
Mean	244	278	351	307	385
StdDev	56	55	73	89	100
Min	155	181	231	155	188
Median	246	280	350	310	423
Max	356	359	501	464	468
Q1	196	235	293	258	381
Q3	288	324	409	369	428

## 5.18 Repeat AF Ablation Procedures

Repeat AF ablations(s) may be performed at the discretion of the physician. The follow-up schedule (Medication Adjustment and Therapy Consolidation periods and exam intervals) will continue based on the initial AF ablation procedure performed, regardless of repeat ablations.

The following assessments should be performed before each procedure:

- Imaging for detection of LA thrombus performed within 48 hours prior to the procedure (refer to Section 5.3 for details).
- Pregnancy Test Pre-menopausal women only, performed within 24 hours prior to the procedure.

#### 5.19 Core Laboratory

A core laboratory will be used for objective evaluation of the TTMs and 24 Hr Holter for the evaluation of recurrence of atrial tachyarrhythmias. Evaluations will be reviewed by a physician. AF episodes will be evaluated per the definition included in this protocol.

#### 6. ADVERSE EVENTS

#### 6.1 Adverse Event Recording

An Adverse Event is any untoward medical occurrence, unintended disease or injury, or untoward clinical signs (including abnormal laboratory findings) occurring during a clinical study, whether or not related to the study device or ablation procedure.

Adverse events will be collected from signing of informed consent throughout study follow-up, at each evaluation and whenever the physician becomes aware of an event. Investigators will determine, at each encounter, whether any adverse events (AE) have occurred, and judge their seriousness and relationship to the study device and procedure.

All adverse events, regardless of classification, seriousness, intensity, outcome, or causality, must be recorded in the electronic CRF(s) in a timely manner throughout the study. Onset date of the event, its treatment, current status (resolved, stabilized, or ongoing), and assessment of its seriousness and relationship to the device should be provided when available. All AEs will be monitored until they are resolved or stabilized (no further changes anticipated).

AF recurrence by itself is considered a recurrence of disease (pre-existing condition), and, therefore, does **not** meet the definition of an AE. Recurrence of pre-existing AFL/AT is also considered recurrence of disease, and not an AE.

The following additional clinical events will not be considered adverse events for this clinical study:

- Minor pericarditis attributable to the ablation procedure defined as pleuritic chest discomfort with or without pericardial rub and ECG changes.
- A trace / trivial / minor pericardial effusion that is asymptomatic, requires no medical intervention, and does not extend hospitalization will not be considered an adverse event.
- AF/AFL/AT recurrence requiring pharmacological or synchronized electrical cardioversion during the hospitalization for the index ablation procedure, or throughout the duration of the study.
- Reablation for AF or pre-existing AFL/AT.

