#### 4.2 Secondary Endpoints

#### 4.2.1 Secondary Effectiveness Endpoints

- Acute Procedural Success
  - o % of subjects with ipsilateral PVI (entrance block) at the end of the procedure
  - % of subjects with ipsilateral PV isolation (entrance block) after first encirclement (evaluated prior to the 30-minute waiting period and adenosine challenge)
  - o % of touch-up (ablation of acute reconnection) among all targeted veins
  - Anatomical location of acute PV reconnection after first encirclement
- Repeat ablation procedures during 12-month period post-procedure
  - Incidence (%) of repeat ablation procedures
  - o % PVs re-isolated among all of the targeted PVs at repeat procedure
  - % repeat ablation procedures requiring new linear lesions and/or identifying new foci outside of initially isolated area among the repeat ablation procedures

- 12-Month Single Procedure Success
  - The 12-month single procedure success is defined as freedom from documented AF/AFL/AT recurrence (episodes ≥ 30 secs) during the Evaluation Period after a single ablation procedure and off AADs. Any repeat ablation procedure or AAD therapy will be deemed effectiveness failure for this analysis.

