## Table 6-2 Anticipated Adverse Events

	Anticipated Adverse Events
1.	Acute Respiratory Distress Syndrome (ARDS)
2.	Air embolism
3.	Allergic reaction
4.	Anaphylactic shock
5.	Anemia
6.	Allergic reaction to Anesthesia (e.g., hair loss)
7.	Apnea - sedation induced
8.	Arrhythmia: bradycardia
9.	Arrhythmia: tachycardia
10.	Arrhythmia: pro-arrhythmias
11.	Arrhythmia: ventricular tachyarrhythmia / pro-arrhythmia
12.	Aspiration pneumonia
13.	Asthmatic attack
14.	Atelectasis
15.	Atrial fibrillation
16.	Exacerbation of pre-existing arrhythmia
17.	Atrio-Esophageal fistula
18.	Typical Atrial flutter
19.	Atypical left atrial flutter
20.	Atypical right atrial flutter
21.	AV fistula
22.	Bleeding complications
23.	Bleeding requiring transfusion
24.	Cardiac arrest
25.	Cardiac perforation
26.	Tamponade
27.	Cardiac thrombo-embolism
28.	Cerebro-vascular accident (CVA) / stroke
29.	Chest pain/discomfort
30.	Complete heart block, temporary or permanent
31.	Conduction block: ongoing / resolved
32.	Congestive Heart Failure
33.	Coronary artery dissection
34.	Coronary artery occlusion
35.	Coronary artery spasm
36.	Coronary artery Thrombosis
37.	Death
38.	Deep venous thrombosis
39.	Dislodgement of ICD (Implantable Cardioverter Defibrillator)
40.	Dislodgement of permanent pacing leads
41.	Disseminated Intravascular Coagulation
42.	Dyspnoea

	Anticipated Adverse Events
43.	Endocarditis
44.	Epistaxis
45.	Esophageal perforation
46.	Expressive aphasia
47.	Fainting
48.	Fatigue
49.	Gastro-intestinal NOS
50.	Gastric reflux
51.	Nausea
52.	Gastrointestinal diverticulosis
53.	Heart Failure
54.	Hematoma (local) /ecchymosis
55.	Hemorrhage
56.	Hemothorax
57.	High / increased creatine phosphokinase (CPK)
58.	Hypotension
59.	Hypertension
60.	Нурохіа
61.	Infection, localized
62.	Infection, systemic
63.	Laceration
64.	Leakage of air or blood into the lungs or other organs due to perforation
65.	Liver toxicity
66.	Mobile strands in Inferior Vena Cava
67.	Myocardial Infarction
68.	Neurological disorders (tremor)
69.	Neurological disorders (poor coordination)
70.	Neurological disorders (headache)
71.	Obstruction to the vascular system
72.	Perforation of the vascular system
73.	Damage to the vascular system
74.	Pericardial effusion resulting in tamponade
75.	Pericardial effusion without tamponade
76.	Pericarditis
77.	Peripheral embolus
78.	Peripheral nerve injury
79.	Peripheral thromboembolism
80.	Phlebitis
81.	Phrenic nerve damage
82.	Diaphragmatic paralysis
83.	Pleural effusion

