#### 5.2.2 Secondary Safety Endpoints

#### • 12-Month PAE Rate:

12-Month PAE Rate is the cumulative incidence of primary adverse events occurring within seven (7) days following an AF ablation procedure using study catheters with EPU and any late onset atrio-esophageal fistula or PV stenosis through 12 months

- Incidence of Unanticipated Adverse Device Effects (UADEs)
- Incidence of Serious Adverse Events (SAEs) within 7 days (early onset), >7 to 30 days (peri-procedural) and >30 days (late onset) of initial ablation
- Incidence of bleeding complication (ISTH definitions): a) major bleeding, b) clinically relevant non-major and c) minor bleeding

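### Protocol 6.1 exempts only pre-existing flutter and tachycardia in two places but all cardioverted AF/AFL/AT recurrence in a third, so a cardioverted new-onset AFL/AT may or may not be counted as an SAE (minor)

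*Protocol*

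**What the plan says.** Protocol 6.1 (Adverse Event Recording) deals with post-ablation arrhythmia in three places.

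- The paragraph before the list says that AF recurrence taken alone is not an AE, then adds for flutter and tachycardia: "Recurrence of pre-existing AFL/AT is also considered recurrence of disease, and not an AE".
- The cardioversion bullet, in a list of further events that do not count as AEs, covers AF/AFL/AT recurrence "requiring pharmacological or synchronized electrical cardioversion during the hospitalization for the index ablation procedure, or throughout the duration of the study". It has no pre-existing condition.
- The reablation bullet, next in the same list, exempts reablation "for AF or pre-existing AFL/AT".

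Protocol 6.3 makes an AE serious if it needs in-patient hospitalization or prolongs an existing one. Protocol 4.2.2 and SAP 5.2.2 name as a secondary safety endpoint the "Incidence of Serious Adverse Events (SAEs) within 7 days (early onset), >7 to 30 days (peri-procedural) and >30 days (late onset) of initial ablation". SAP 5.2 and 9.5 make it descriptive, with no hypothesis. Protocol 6.13 sends primary AEs and cardiac SAEs to the Clinical Events Committee (CEC).

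**The concern.** An event must be an AE before it can be an SAE. If 6.1 gives two answers for the same arrhythmia, two of the up to 45 sites can code the same admission differently and both be following the protocol. The SAE percentages then mix two definitions, and a single-arm study has no control group in which the same mixing would occur.

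The affected event is a flutter or tachycardia that the subject did not have before ablation. A safety table should show it, because it may be a consequence of the procedure. The effectiveness endpoint does not always show it instead. In Protocol 4.1.1, arrhythmia recurrence counts only on Days 91-365 and DC cardioversion only after the blanking period. The >7 to 30 day SAE window lies wholly inside blanking. A new-onset flutter cardioverted on Day 20 and treated as exempt would be neither an SAE nor, by itself, an effectiveness failure.

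**Working it through.** The plan gives no figure on this point to reproduce. The check is a comparison of the rules, followed by a bound.

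**Step 1. Meaning of recurrence.** Protocol 4.2.1 defines 12-month single procedure success by "freedom from documented AF/AFL/AT recurrence" lasting at least 30 seconds, and 4.1.1 uses the word in the same way. Neither requires that the flutter or tachycardia existed before ablation. In the protocol's endpoint vocabulary, a first-ever flutter after ablation is therefore a recurrence.

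**Step 2. Apply each line of 6.1 to each case.**

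| Event after ablation | Paragraph | Cardioversion bullet | Reablation bullet |
|---|---|---|---|
| AF, cardioverted | not an AE | not an AE | not relevant |
| Pre-existing AFL/AT, cardioverted | not an AE | not an AE | not relevant |
| New-onset AFL/AT, no cardioversion | AE | does not apply | not relevant |
| New-onset AFL/AT, reablated, no cardioversion | AE | does not apply | not exempt |
| New-onset AFL/AT, cardioverted | AE | exempt, if recurrence has its endpoint meaning | not relevant |

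Only the last row is in conflict. The same new-onset flutter is an AE if reablated but may not be one if cardioverted, and no text says which line prevails.

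**Step 3. Follow it to the endpoint.** Admission makes the event an SAE under 6.3 if it is an AE, and nothing if it is exempt. The CEC sees reported events, so an event that a site has treated as exempt does not reach it. Table 6-1 contains no atrial arrhythmia, so the primary safety count cannot change. The effectiveness endpoint does not use AE status. Power and type I error concern those two endpoints only.

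**Step 4. Bound the shift.**

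- Treated subjects: 330 enrolled less about 30 not treated (Protocol Summary; SAP 8) = 300.
- r = share of subjects admitted with new-onset AFL/AT. Assumption: 1-3%.
- c = fraction of those who are cardioverted; s = fraction at sites that follow the bullet. Neither is given.
- Shift in SAE incidence, if the admission is the subject's only SAE in the window = r × c × s.
- Upper bound, c = s = 1: 1 to 3 points. 0.01 × 300 = 3 and 0.03 × 300 = 9 subjects.
- Illustration, c = s = 0.5: 0.01 × 0.25 = 0.25 points and 0.03 × 0.25 = 0.75 points, or about 1 to 2 subjects.

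For scale, if the SAE rate were 10% (assumption), its standard error would be √(0.10 × 0.90 / 300) = 0.0173, or 1.7 points. The upper bound is then 1/1.73 = 0.6 to 3/1.73 = 1.7 standard errors, and the illustration is 0.1 to 0.4.

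**The case against.** The best defence is that recurrence ordinarily means the return of something already present. The paragraph just above the list uses it that way, since it opens with "AF recurrence by itself is considered a recurrence of disease (pre-existing condition" as its reason. On that reading the cardioversion bullet already covers only pre-existing arrhythmia. This is a fair reading, and probably the intended one. It does not settle the matter: the reablation bullet found it necessary to write the limit out, the list is presented as adding to the paragraph, and the endpoint sections use the word more broadly.

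It is also true that the data are not lost. Arrhythmia occurrence is collected at every follow-up contact, and hospitalizations are recorded. That limits the problem to the AE and SAE tables, but SAE incidence is reported from those tables.

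A reader might infer a wider contradiction from Table 6-2, which lists atrial fibrillation, "Exacerbation of pre-existing arrhythmia" and, among the flutters, "Atypical left atrial flutter". The documents do not support this.

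- Protocol 6.5 presents the table as events seen in earlier RF ablation studies. Under 6.6, its natural use is to separate anticipated from unanticipated effects.
- It is plainly generic. It includes ICD dislodgement although ICD patients are excluded, repeats acute respiratory distress syndrome, and lists pericarditis and effusion without tamponade although 6.1 exempts their minor forms.
- 6.1 exempts AF recurrence only when it stands alone, so some AF can still be an AE. Worsening of a pre-existing arrhythmia need not be atrial. The flutter entries fit 6.1 if they mean new-onset flutter.

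**Conclusion.** The text is wrong as written, and the matter is minor. Protocol 6.1 gives two possible answers for one class of event, the new-onset AFL/AT that is cardioverted. When such a subject is admitted, the SAE count depends on which line the site follows. The effect is confined to AE and SAE tabulations, including a descriptive secondary endpoint. It is at most 1-3 percentage points if 1-3% of subjects are admitted with new-onset AFL/AT, and smaller to the extent that some are not cardioverted or some sites follow the paragraph. That rate is an assumption; the documents give none.

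Two stronger conclusions might be drawn and should not be. New-onset AFL/AT in general is not exempt, because without cardioversion no line of 6.1 exempts it. The study's success decision is not at risk either, because neither primary endpoint depends on this rule.

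**What to change.** 1. In Protocol 6.1, open the cardioversion bullet with *AF or pre-existing AFL/AT recurrence*, so that it matches the paragraph and the reablation bullet.
2. Apply that one rule to all arrhythmia admissions already entered. The arrhythmia history taken before the procedure (Protocol 5.3) provides a basis for deciding what was pre-existing.
3. In SAP 9.5, add one line beside the SAE windows that counts admissions for exempt AF/AFL/AT. The reader can then see the total under either rule.
4. Leave the AF and exacerbation entries in Table 6-2. Removing them could make a reportable, device-related form look unanticipated under 6.6. At most, add a note that the table is subject to the exemptions in 6.1.

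The cost is a wording change in the protocol and the CRF guidance, one table line, and the recoding of arrhythmia admissions already entered. No new visits or data are needed. The reported SAE rate may rise slightly, because cardioverted new-onset AFL/AT that met 6.3 would now be counted at every site.

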#### 6.2 Classification

Any of the following events are to be reported to the sponsor immediately. The Sponsor may request additional information after the initial notification.

## 6.2.1 Primary Adverse Event

A Primary AE is one of the following events occurring within seven (7) days following an AF ablation procedure with the STSF/ST catheter and VISITAG SURPOINTTM module with EPU, except atrio-esophageal fistula and PV stenosis, which may also be considered as primary adverse events if occurring greater than seven (7) days post the ablation procedure .

PRIMARY ADVERSE EVENT	DESCRIPTION / CRITERIA	
Death	Patient death directly related to the device or procedure and occurs at any time during or after the procedure.	
Atrio-Esophageal Fistula	Is defined as a connection between the atrium and the lumen of the esophagus. Evidence supporting this diagnosis includes documentation of esophagus erosion combined with evidence of a fistulous connection to the atrium such as air emboli, an embolic event, or direct observation at the time of surgical repair. A CT or MRI scan is the most common method of documentation of an atrio-esophageal fistula.	
Cardiac Tamponade*+/Perforation+	The development of a significant pericardial effusion during or within 30 days of undergoing an AF ablation procedure. A significant pericardial effusion is one which results in hemodynamic compromise, requires elective or urgent pericardiocentesis, or results in a 1 cm or more pericardial effusion as documented by echocardiography. Cardiac tamponade should also be classified as" early" or "late" depending on whether it is diagnosed during or following initial discharge from the hospital.	
Myocardial Infarction	
 
The presence of any one of the following criteria:
 
Detection of ECG changes indicative of new ischemia (new ST-T changes or new LBBB) which persists for more than 1 h
 
Development of a new pathological Q waves on an ECG, and
 
Imaging evidence of new loss of viable myocardium or new regional wall motion abnormality
 
	

